Follow-up Phase

All subjects who complete the study will return for a follow-up visit (within 4 weeks from last dose) to assess adverse event status and to document concomitant medications.

Number of Subjects (Planned): The number of subjects planned for this study is approximately 15.

Study Entry Criteria:

Inclusion Criteria:

- Male or female subjects ages 21 to 80, inclusive
- Presence of IPF confirmed per ATS criteria (2011)
- Presence of disease, stage I-III defined by GAP index (Gender, Age and Physiology)
- Subjects who are currently treated with OFEVTM (Nintedanib) should be on a stable dose for at least 3 months prior to initiation of the study drug.
- Females of child-bearing potential must have a negative serum β-hCG at screening and must be willing to use appropriate contraception (as defined by the investigator) for the duration of study treatment and 30 days after the last dose of study treatment.
- Males should practice contraception for the duration of study treatment and 30 days after the last dose of study treatment as follows: condom use and contraception by female partner.
- Subject is in stable condition on the basis of medical history, physical examination, and laboratory screening, as determined by the investigator.
- Subject is willing and able to comply with the protocol assessments and visits, in the opinion of the study nurse/coordinator and the Investigator.
- Written informed consent is obtained prior to participating the study.

Exclusion Criteria:

- Expected to receive a lung transplant within 1 year from the start of the Treatment Phase or on a lung transplant waiting list at the start of the Treatment Phase.
- Known explanation for interstitial lung disease
- Subjects on OFEVTM (Nintedanib) with a dose interruption due to significant adverse events within 6 weeks of screening visits.
- Ongoing IPF treatments with investigational therapy
- Ongoing IPF treatments with Esbriet® (Pirfenidone)
- Immunosuppressants (i.e., Mycophenolate, Imuran, Cyclophosphamide), and cytokine modulating agents within 1 month of Screening Visit and throughout the study
- Use of antibiotics and systemic steroids due to IPF exacerbation within 1 month of Screening Visit
- Clinically significant cardiovascular disease, including myocardial infarct within last 6 months, unstable ischemic heart disease, congestive heart failure or angina
- Resting pulse < 50 bpm, SA or AV block, uncontrolled hypertension, or QTcF > 450 ms
- Immune system disease

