6.4. Follow-up Phase

All subjects who complete the study will return for their final visit at 4 weeks after their last dose for safety assessments and to assess adverse event status and document concomitant medications.

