7.2. Inclusion/Exclusion Criteria

7.2.1. Inclusion Criteria

- Male or female subjects ages 21 to 80, inclusive
- Presence of IPF confirmed per ATS criteria (2011)
- Presence of stage I-III defined by GAP index (Gender, Age and Physiology)
- Subjects who are currently treated with OFEVTM (Nintedanib), should be on a stable dose for at least 3 months prior to initiation of the study drug.
- Females of child-bearing potential must have a negative serum β-hCG at screening and must be willing to use appropriate contraception (as defined by the investigator) for the duration of study treatment and 30 days after the last dose of study treatment.
- Males should practice contraception for the duration of study treatment and 30 days after the last dose of study treatment as follows: condom use and contraception by female partner.
- Subject is in stable condition on the basis of medical history, physical examination, and laboratory screening, as determined by the investigator.
- Subject is willing and able to comply with the protocol assessments and visits, in the opinion of the study nurse/coordinator and the Investigator.
- Written informed consent is obtained prior to participating in the study.

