8.8.1.4 Follow-up / Laboratory Re-test Visits/ Early termination visit

Follow up clinic visit: Month 13 (\pm 5 days)

- Physical examination
- Body weight
- Vital signs including supine blood pressure, respiratory rate, heart rate, and temperature
- Adverse event review
- Concomitant medication review

Laboratory Re-test visit

Subjects who have clinically significant abnormal lab finding will return for a laboratory re-test visit and will have the following assessments performed:

- Fasting chemistry, hematology, or urinalysis lab, as indicated
- Adverse event review
- Concomitant medication review

Early Termination visit

Subjects who discontinued study medication will undergo the following assessments:

- Physical examination
- Body weight
- Vital signs including supine blood pressure, respiratory rate, heart rate, and temperature
- Adverse event review
- Concomitant medication review
- Patient diary review and collect
- Study drug accountability
- Study drug return
- 12-lead ECG**
- Fasting safety labs chemistry (including CPK, liver enzymes, lipid panel) hematology, and urinalysis labs**
- Urine β-hCG (pre-menopausal females)**
- Blood Sample for biomarker**
- Pulmonary function test**
- 6MWT**7
- Dyspnea score (MMRC)**
- ATAQ-IPF**
 - ** Assessment need not be performed if prior assessment occurred within 1 month of Early Termination Visit.

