8.8.2.12. Adverse Event (AE) Monitoring

The PI or a qualified designee listed on Form FDA 1572 must assess the severity and relationship to study medication for all AEs (see Section 12.2).

All observed or volunteered AEs regardless of treatment group or suspected causal relationship to the investigational product(s) will be recorded on the AE page(s) of the CRF.

Each PI and research team are responsible for identifying adverse events and reporting them.

For all AEs, the Investigator must pursue and obtain information adequate to determine the outcome of the AE and to assess whether it meets the criteria for classification as an SAE (see Section 5) requiring immediate notification to the Sponsor or its designated representative.

For all AEs, sufficient information should be obtained by the Investigator to determine the causality of the AE. The Investigator is required to assess causality and indicate that assessment on the CRF. For AEs with a causal relationship to the investigational product, follow-up by the Investigator is required until the event or its sequelae resolve or stabilize at a level acceptable to the Investigator, and Sponsor concurs with that assessment.

Adverse events (serious and non-serious) including all suspected unexpected serious adverse reactions (SUSARs) should be recorded on the CRF from the date of informed consent until the end of their participation in the study (i.e., the subject has discontinued or completed the follow-up visit).

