12.3. Recording Adverse Events

Adverse events should be collected and recorded for each subject from the date that the first study dose was taken until the end of their participation in the study (i.e., the subject has discontinued or completed the study). Only those AEs that occurred while on study drug that have not been resolved will be followed until resolution or stabilization.

Following the end of the subject's participation in the study, the PI or an authorized delegate should report SAEs "spontaneously" if considered at least possibly related to study medication.

Adverse events may be volunteered spontaneously by the study subject, or discovered by the study staff during physical examinations or by asking an open, non-leading question such as, "How have you been feeling since you were last asked?" All AEs and any required remedial action will be recorded in the subject's source documentation and transcribed onto the appropriate CRF page for the study period indicated. The nature of AE, date (and time, if known) of AE onset, date (and time, if known) of AE outcome to date, severity, and action taken of the AE will be documented together with the PIs or an authorized physician's assessment of the seriousness of the AE and causal relationship to study medication and/or study procedure (at the time of assessment).

All AEs should be recorded individually in the study subject's own words (verbatim) unless, in the opinion of the PI or an authorized physician, the AEs constitute components of a recognized condition, disease, or syndrome. In the latter case, the condition, disease, or syndrome should be named rather than each individual symptom. The AEs will subsequently be coded using the MedDRA.

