13.1.4. Safety Analysis

Safety analyses will be conducted on the Safety Analysis Set.

The incidence of treatment-emergent AEs (TEAEs, defined as AEs occurring from the time of first dose through 7 days after the last dose of study medication), SAEs and AEs leading to discontinuations will be summarized by treatment group. Incidence of TEAEs will also be summarized by severity (mild, moderate, or severe), as well as by relationship to treatment (not related, possibly related, or probably related) and by seriousness.

Changes from baseline in laboratory values will be summarized by treatment groups for continuous variables. Lab shift tables showing incidence of new or worsening clinically significant findings from baseline to the last visit will be displayed by treatment groups. Shift from baseline to the highest lab value, and from baseline to the lowest lab value will also be displayed.

Incidence of out-of-normal-range values and markedly abnormal change from baseline in laboratory safety test variables will be tabulated by treatment group.

Changes in vital signs from baseline to each visit will be summarized by treatment groups.

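### Subjects who stop early may go partly or wholly unobserved for new adverse events during the 7 days after the last dose that the protocol counts as treatment-emergent

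*Protocol*

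**What the plan says.** **Who is seen after the last dose.** Protocol section 6.4: "All subjects who complete the study will return for their final visit at 4 weeks after their last dose for safety assessments". The follow-up paragraph of the synopsis has the same restriction to completers but a different timing: "All subjects who complete the study will return for a follow-up visit (within 4 weeks from last dose"). Table 1 and section 8.8.1.4 place the visit at Month 13 with a 5-day margin either way.

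**When AE recording ends.** Section 8.8.2.12 ends it when "the subject has discontinued or completed the follow-up visit". Section 12.3 collects AEs "until the end of their participation in the study (i.e., the subject has discontinued or completed the study"). In both, discontinuation closes collection.

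**What counts as treatment-emergent.** Section 13.1.4: "AEs occurring from the time of first dose through 7 days after the last dose of study medication". SAP section 14.1 replaces this with any AE during or after the first administration and lists AEs 7 days after the last dose separately. SAP section 15 declares the definition change as a departure.

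**What early stoppers get.** Section 8.8.1.4, under the Early Termination visit: "Subjects who discontinued study medication will undergo the following assessments". The list includes AE review, physical examination, vital signs and concomitant medication review, plus ECG and laboratory tests unless done within the previous month. Section 7.3 asks for these procedures at the time of study discontinuation, on a best-effort basis. No day relative to the last dose is given.

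**What continues after that.** AEs present at discontinuation are followed (sections 7.3.3 and 12.3). After participation ends, serious AEs (SAEs) are reported spontaneously, and only if judged at least possibly related (sections 12.3 and 12.5.1).

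**The concern.** The analysis definition and the collection rule do not match. The protocol states a 7-day post-dose window for treatment-emergent events, then lets recording stop at discontinuation and schedules nothing across that week for anyone who does not complete. The individual stopping criteria in section 7.3.1 remove the subject from the study, not only from study drug, so a subject who meets them falls under this rule.

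At stake is the completeness of the safety record in the subjects whose first days off drug are of most interest. A new event in that week that is non-serious, or serious but first judged unrelated, has no planned route into the database. In the randomized phase, an off-drug window within the study arises only through early stopping, because subjects who finish that phase continue directly on open-label MN-001 (sections 6.3 and 8.8.1.2).

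**Working it through.** There is no plan figure to reproduce: the sample size of about 15 is given without rate, power or dropout inputs (section 13.1.3). The check sets the rules side by side and then sizes the gap.

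**Step 1: which rule could capture a new AE in days 1 to 7 after the last dose of an early stopper?**

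| Provision | Captures a new post-dose AE? |
|---|---|
| Follow-up visit (synopsis, 6.4) | No; completers only |
| AE recording (8.8.2.12, 12.3) | Only up to discontinuation |
| Early Termination visit (7.3, 8.8.1.4) | Only events before the visit; day not set |
| Follow-up of existing AEs (7.3.3, 12.3) | No; only AEs already present |
| SAEs after participation (12.3, 12.5.1) | Only if serious, at least possibly related and spontaneously reported |
| SAP 14.1 and 15 | No; changes classification and listing, adds no collection |

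**Step 2: days left uncovered.** Take the reading more favourable to the plan, that recording runs through the Early Termination visit. If that visit falls d days after the last dose, the uncovered share of the window is (7 − d)/7 for d up to 7, and zero after that.

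- d = 0: 7/7 = 100%
- d = 1: 6/7 = 86%
- d = 3: 4/7 = 57%
- d = 5: 2/7 = 29%
- d = 7 or later: 0%

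**Step 3: how many subjects might this touch?** No early-stopping rate is given for this trial. The rates below come from protocol section 4.2.1 and Table 4, in other populations, on shorter treatment and partly at other doses. They illustrate scale and do not predict. With n = 15, the expected number of early stoppers is 15p and P(at least one) = 1 − (1 − p)^15.

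| Rate used | p | Expected of 15 | P(at least one) |
|---|---|---|---|
| Stopped for an AE, KCA-757-T201: 11/112 | 9.8% | 1.5 | 0.79 |
| Did not complete, MN-001-CL-001: (147 − 131)/147 = 16/147 | 10.9% | 1.6 | 0.82 |
| Did not complete, MN-001-CL-002: (305 − 251)/305 = 54/305 | 17.7% | 2.7 | 0.95 |
| Assumed low | 5% | 0.75 | 0.54 |
| Assumed high | 30% | 4.5 | 0.995 |

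Table 4 gives 108 rather than 112 subjects for KCA-757-T201; 11/108 = 10.2% makes no material difference. These are counts of early stoppers, not of missed events.

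**Step 4: which outputs can change?** SAP 14.1 counts each subject once at subject, system organ class and preferred-term level. A subject who stops because of an AE that began on drug is therefore already in the overall treatment-emergent proportion and in discontinuations due to such events. A second, uncollected AE leaves both unchanged. It can change the serious-event proportion, the deaths listing, a system organ class or preferred-term row, or a severity row. The overall proportion moves only if the early stopper had no earlier treatment-emergent AE, which means someone who stopped for another reason.

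**The case against.** The strongest reply is that early stoppers are not abandoned. They have an Early Termination visit with AE review, every effort is to be made to complete it, AEs present at discontinuation are followed, and SAEs are followed to resolution (section 12.4). Section 12.1 also says events in post-treatment follow-up periods are to be recorded. This stands as far as it goes, and it is why the conclusion is that events may be missed rather than will be. It does not close the gap. The visit is not tied to the last dose, the follow-up provisions concern events already known, and no post-treatment follow-up period is defined for subjects who do not complete.

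Four stronger readings are tempting and are not supported.

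- *The gap biases the safety comparison in favour of MN-001.* This would need more early stopping on MN-001 and missed events that change a reported proportion. The documents give no stopping rate for this trial, and a subject who stops for an on-drug AE is already counted.
- *One missed event shifts the MN-001 proportion by 10 percentage points.* With about 10 MN-001 subjects, 1/10 is the right arithmetic, but only for a subject not already counted in that row.
- *Completers are observed off drug for about 25 to 35 days (a month of about 30 days, plus or minus 5) against none for early stoppers.* The Month 13 visit belongs to the open-label phase (SAP 10.2), which is analysed separately (SAP 14) and has no concurrent placebo arm. The days beyond day 7 also lie outside the protocol's window.
- *The SAP abandons the 7-day limit.* It drops the limit from the definition but keeps a separate listing at 7 days after the last dose.

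The 30-day contraception requirement in section 7.2.1 raises a separate question about pregnancy reporting. Visit 14 includes no pregnancy assessment, so that question is not part of this point.

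**Conclusion.** The concern holds as a gap in collection. For an early stopper, anywhere from none to all of the protocol's 7-day post-dose window can pass without planned collection of new AEs, depending only on when the Early Termination visit happens to fall. The events exposed are new SAEs or deaths (unless spontaneously reported and judged at least possibly related), preferred-term and severity entries, and first AEs in subjects who stop for non-AE reasons. The overall treatment-emergent proportion is largely unaffected for subjects who stop because of an on-drug AE.

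This rests on reading discontinuation as the end of recording, as sections 8.8.2.12 and 12.3 say, extended to the Early Termination visit in the plan's favour. Neither a rate of early stopping nor a direction of bias can be stated for this trial. The point is worth acting on because the remedy is small and the safety record comes from only about 15 subjects.

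**What to change.** 1. In protocol sections 8.8.2.12 and 12.3, state that AE collection for every dosed subject, including those who discontinue, runs to at least 7 days after the last dose.
2. Schedule one safety contact (AE and concomitant medication review, by telephone if needed) at or after that point, timed from the last dose, for subjects who stop early. Add it to section 8.8.1.4 and Table 1.
3. Reconcile the follow-up visit timing, which differs between the synopsis and section 6 (within 4 weeks), section 6.4 (at 4 weeks) and section 8.8.1.4 with Table 1 (Month 13 plus or minus 5 days).
4. Align the post-dose wording in SAP 14.1 with the protocol window. State whether the separately listed AEs are those after day 7, and whether they are also included in the summary tables.

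If data collection has already closed, report for each early stopper the last-dose date, the last AE contact and the number of the 7 days observed.

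The cost is protocol and SAP wording plus one extra contact per early stopper: 0.75 to 4.5 contacts expected over the assumed 5% to 30% range. A subject who withdraws consent may still be out of reach, and the report should say so.

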7. SELECTION AND WITHDRAWAL OF SUBJECTS

7.1. Clinical Trial Population

The population for this trial will include male and female subjects ≥ 21 and ≤ 80 years of age with a confirmed diagnosis of IPF.

7.2. Inclusion/Exclusion Criteria

7.2.1. Inclusion Criteria

- Male or female subjects ages 21 to 80, inclusive
- Presence of IPF confirmed per ATS criteria (2011)
- Presence of stage I-III defined by GAP index (Gender, Age and Physiology)
- Subjects who are currently treated with OFEVTM (Nintedanib), should be on a stable dose for at least 3 months prior to initiation of the study drug.
- Females of child-bearing potential must have a negative serum β-hCG at screening and must be willing to use appropriate contraception (as defined by the investigator) for the duration of study treatment and 30 days after the last dose of study treatment.
- Males should practice contraception for the duration of study treatment and 30 days after the last dose of study treatment as follows: condom use and contraception by female partner.
- Subject is in stable condition on the basis of medical history, physical examination, and laboratory screening, as determined by the investigator.
- Subject is willing and able to comply with the protocol assessments and visits, in the opinion of the study nurse/coordinator and the Investigator.
- Written informed consent is obtained prior to participating in the study.

7.2.2. Exclusion Criteria

- Expected to receive a lung transplant within 1 year from the start of the Treatment Phase or on a lung transplant waiting list at the start of the Treatment Phase.
- Known explanation for interstitial lung disease
- Subjects on OFEVTM (Nintedanib) with dose interruption due to significant adverse events within 6 weeks of screening visits.
- Ongoing IPF treatments with investigational therapy
- Ongoing IPF treatment with Esbriet® (Pirfenidone)
- Immunosuppressants (i.e., Mycophenolate, Imuran, Cyclophosphamide), and cytokine modulating agents within 1 month of Screening Visit and throughout the study
- Use of antibiotics and systemic steroids due to IPF exacerbation within 1 month of Screening Visit
- Clinically significant cardiovascular disease, including myocardial infarct within last 6

- months, unstable ischemic heart disease, congestive heart failure or angina
- Resting pulse < 50 bpm, SA or AV block, uncontrolled hypertension, or QTcF > 450 ms
- Immune system disease
- Any significant laboratory abnormality which, in the opinion of the Investigator, may put the subject at risk
- History of malignancy < 5 years prior to signing the informed consent, except for adequately treated basal cell or squamous cell skin cancer or in situ cervical cancer.
- History or evidence of drug or alcohol abuse
- History of HIV (human immunodeficiency virus) or other active infection.
- Currently has a clinically significant medical condition including the following: neurological, psychiatric, metabolic, hepatic, hematological, pulmonary (other than IPF), cardiovascular (including uncontrolled hypertension), gastrointestinal, urological disorder, or central nervous system (CNS) infection that would pose a risk to the subject if they were to participate in the study or that might confound the results of the study.

Note: Active medical conditions that are minor or well-controlled are not exclusionary if, in the judgment of the Investigator, they do not affect risk to the subject or the study results. In cases in which the impact of the condition upon risk to the subject or study results is unclear, the Medical Monitor should be consulted.

- CYP2C8 and CYP2C9 substrates with narrow therapeutic indices (i.e., paclitaxel, phenytoin and S-warfarin) within 14 days of Screening Visit and throughout the study.
- Macrolide or quinolone class antibiotics within 14 days of Screening Visit and throughout the study.
- Poor peripheral venous access that will limit the ability to draw blood as judged by the Investigator.
- Currently participating, or has participated in, a study with an investigational or marketed compound or device within 3 months prior to signing the informed consent.
- Unwilling or unable to conduct Vital Capacity test.
- Unable to cooperate with any study procedures, unlikely to adhere to the study procedures and keep appointments, in the opinion of the Investigator, or is planning to relocate during the study.

